10.3.6.5. Assessment of Causality

- The PI/investigator is obligated to assess the relationship between study intervention and each occurrence of each AE/SAE.

- A 'reasonable possibility' of a relationship conveys that there are facts, evidence, and/or arguments to suggest a causal relationship, rather than a relationship cannot be ruled out.
- The PI/investigator will use clinical judgement to determine the relationship.
- Alternative causes, such as underlying disease(s), concomitant therapy, and other risk factors, as well as the temporal relationship of the event to study intervention administration will be considered and investigated.
- The PI/investigator will also consult the Investigator's Brochure in his/her assessment.
- For each AE/SAE, the PI/investigator must document in the medical notes that he/she has reviewed the AE/SAE and has provided an assessment of causality.
- There may be situations in which an SAE has occurred, and the PI/investigator has minimal information to include in the initial report to the sponsor's pharmacovigilance (PV) provider. However, it is very important that the PI/investigator always assesses causality for every event before the initial transmission of the SAE data to sponsor's PV provider.
- The PI/investigator may change his/her opinion of causality considering follow-up information and send an SAE follow-up report with the updated causality assessment.
- The causality assessment is one of the criteria used when determining regulatory reporting requirements.

The relationship of an AE to the IMP will be categorised as shown in [Table 10-3](#):

Table 10-3: Classification of Adverse Events Relationship

Classification	Definition
Not related	The AE is related to an aetiology other than the IMP (the alternative aetiology must be documented in the participant's medical record).
Unlikely to be related	The AE is unlikely to be related to the IMP and likely to be related to factors other than IMP.
Possibly related	There is an association between the AE and the administration of the IMP, and there is a plausible mechanism for the AE to be related to the IMP, but there may also be alternative aetiology, such as characteristics of the participant's clinical status or underlying disease.

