Tables presented by relationship will only include the subset of adverse events that are judged as being 'Related' to IMP or challenge agent, i.e. correspond to adverse events where relationship is recorded on the adverse event page as being 'Unlikely', 'Possibly', 'Probably', 'Definitely', or a relationship is not given.

In all AE summary tables results will be displayed ordered in terms of decreasing frequency of SOC occurrence (based on total across all participants), and within each SOC also ordered in terms of decreasing frequency of preferred term occurrence (also based on total across all participants). In all AE summary tables a total column including data across all participants will also be presented.

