Note: If a participant experiences more than one event, then the event with the worst severity or strongest relationship is included in the relevant level of summarisation.

Note: Related = 'Unlikely', 'Possibly', 'Probably', 'Definitely' or 'Not assessed'.

Note: Adverse Event Leading to Discontinuation from the Study = Participant withdrew from the study due to an adverse event.

Note: Adverse Event Leading to Discontinuation of Dosing = Action taken of 'Trial/Study drug permanently discontinued'.

Note: Percentages are based on the safety population.

Table 14.3.1.68
 Treatment Emergent Adverse Events by System Organ Class and Preferred Term
 Safety Population

System Organ Class/ Preferred Term [1]	Treatment Group			
	RV299 (N=xx)	n (%)	Placebo (N=xxx)	n (%)
Number of Events	XX		XX	
Number of Subjects with any adverse event	XX	(XX.X)	XX	(XX.X)
System Organ Class 1	XX	(XX.X)	XX	(XX.X)
Preferred Term 1	XX	(XX.X)	XX	(XX.X)
Preferred Term 2	XX	(XX.X)	XX	(XX.X)
System Organ Class 2	XX	(XX.X)	XX	(XX.X)
Preferred Term 1	XX	(XX.X)	XX	(XX.X)
Preferred Term 2	XX	(XX.X)	XX	(XX.X)

[1] MedDRA Version 25.0.

Note: Treatment emergent events are those events with an onset on or after the first administration of IMP.

Note: Table shows distinct number of participants with events for each system organ class/preferred term.

Note: Percentages are based on the safety population.

Table 14.3.1.3
Treatment Emergent Adverse Events by System Organ Class, Preferred Term and Severity
Safety Population

System Organ Class/ Preferred Term [1]	Treatment Group			
	RV299 (N=xx)	n (%)	Placebo (N=xxx)	n (%)
System Organ Class 1				
Mild	XX	(XX.X)	XX	(XX.X)
Moderate	XX	(XX.X)	XX	(XX.X)
Severe	XX	(XX.X)	XX	(XX.X)
Preferred Term 1				
Mild	XX	(XX.X)	XX	(XX.X)
Moderate	XX	(XX.X)	XX	(XX.X)
Severe	XX	(XX.X)	XX	(XX.X)
Preferred Term 2				
Mild	XX	(XX.X)	XX	(XX.X)
Moderate	XX	(XX.X)	XX	(XX.X)
Severe	XX	(XX.X)	XX	(XX.X)
System Organ Class 2				
Mild	XX	(XX.X)	XX	(XX.X)
Moderate	XX	(XX.X)	XX	(XX.X)
Severe	XX	(XX.X)	XX	(XX.X)
Preferred Term 1				
Mild	XX	(XX.X)	XX	(XX.X)
Moderate	XX	(XX.X)	XX	(XX.X)
Severe	XX	(XX.X)	XX	(XX.X)

[1] MedDRA Version 25.0.

Note: Treatment emergent events are those events with an onset on or after the first administration of IMP.

Note: This table shows distinct number of participants with events for each system organ class/preferred term/severity. If a participant experienced a specific event more than once then the event with the worst severity is summarised.

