Note: Percentages are based on the safety population.

Table 14.3.1.4
Treatment Emergent Adverse Events Related to RV299 by System Organ Class and Preferred Term
Safety Population

System Organ Class/ Preferred Term [1]/ Relationship	Treatment Group			
	RV299 (N=xx)	n (%)	Placebo (N=xxx)	n (%)
System Organ Class 1	XX	(XX.X)	XX	(XX.X)
Not Assessed	XX	(XX.X)	XX	(XX.X)
Unlikely Related	XX	(XX.X)	XX	(XX.X)
Possibly Related	XX	(XX.X)	XX	(XX.X)
Probably Related	XX	(XX.X)	XX	(XX.X)
Definitely Related	XX	(XX.X)	XX	(XX.X)
Preferred Term 1	XX	(XX.X)	XX	(XX.X)
Not Assessed	XX	(XX.X)	XX	(XX.X)
Unlikely Related	XX	(XX.X)	XX	(XX.X)
Possibly Related	XX	(XX.X)	XX	(XX.X)
Probably Related	XX	(XX.X)	XX	(XX.X)
Definitely Related	XX	(XX.X)	XX	(XX.X)
Preferred Term 2	XX	(XX.X)	XX	(XX.X)
Not Assessed	XX	(XX.X)	XX	(XX.X)
Unlikely Related	XX	(XX.X)	XX	(XX.X)
Possibly Related	XX	(XX.X)	XX	(XX.X)
Probably Related	XX	(XX.X)	XX	(XX.X)
Definitely Related	XX	(XX.X)	XX	(XX.X)
System Organ Class 2	XX	(XX.X)	XX	(XX.X)
Not Assessed	XX	(XX.X)	XX	(XX.X)
Unlikely Related	XX	(XX.X)	XX	(XX.X)
Possibly Related	XX	(XX.X)	XX	(XX.X)
Probably Related	XX	(XX.X)	XX	(XX.X)
Definitely Related	XX	(XX.X)	XX	(XX.X)
Preferred Term 1	XX	(XX.X)	XX	(XX.X)
Not Assessed	XX	(XX.X)	XX	(XX.X)
Unlikely Related	XX	(XX.X)	XX	(XX.X)
Possibly Related	XX	(XX.X)	XX	(XX.X)
Probably Related	XX	(XX.X)	XX	(XX.X)
Definitely Related	XX	(XX.X)	XX	(XX.X)

[1] MedDRA Version 25.0.

Note: Treatment emergent events are those events with an onset on or after the first administration of IMP.

Note: This table shows distinct number of participants with events for each system organ class/preferred term/relationship. If a participant experiences a specific event more than once then the event with the greatest relationship is summarised.

Note: Only the subset of AEs that are judged to be related to IMP have been considered (i.e. relationship = Possibly Related/Probably Related/Definitely Related/Not Assessed) in the table.

Note: Percentages are based on the safety population.

This layout will be utilised for the following table:

Table 14.3.1.5 Adverse Events Related to Challenge Agent by System Organ Class and Preferred Term - Safety Population

With the following footnote:

Note: Only the subset of AEs that are judged to be related to challenge agent have been considered (i.e. relationship = Possibly Related/Probably Related/Definitely Related/Not Assessed) in the table.

Table 14.3.2
Haematology Parameters: Summary
Safety Population

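### The SAP gives two conflicting definitions of a 'related' adverse event: one counts events rated 'Unlikely', the other leaves them out

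*SAP*

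**What the plan says.** Protocol Section 10.3.6.5 (Table 10-3) gives a five-level scale for relationship to the IMP. It defines the second level in these words: "The AE is unlikely to be related to the IMP and likely to be related to factors other than IMP". The protocol does not say where on the scale 'related' begins.

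The SAP draws that line in several places:

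- Section 10.9.1, on content: "Tables presented by relationship will only include the subset of adverse events that are judged as being 'Related' to IMP or challenge agent".
- Section 10.9.1, on which ratings qualify: "relationship is recorded on the adverse event page as being 'Unlikely', 'Possibly', 'Probably', 'Definitely', or a relationship is not given".
- Overall TEAE summary shell (Table 14.3.1.1 in the list of tables), footnote: "Related = 'Unlikely', 'Possibly', 'Probably', 'Definitely' or 'Not assessed".
- Table 14.3.1.4 shell, footnote: "relationship = Possibly Related/Probably Related/Definitely Related/Not Assessed". The same wording is prescribed for Table 14.3.1.5, which covers the challenge agent.
- Table 14.3.1.4 shell, body: a row labelled "Unlikely Related" under each system organ class and preferred term. Table 14.3.1.5 uses the same layout.

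SAP Section 11 lists six changes from the protocol analysis. None concerns causality.

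**The concern.** A programmer cannot satisfy the body and the footnote of Table 14.3.1.4 together. If the footnote governs, the 'Unlikely' rows must be empty. If the rows are filled, the footnote is false. The text of Section 10.9.1 supports the rows, so the choice would be made during programming rather than in the plan.

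The inclusive rule is also awkward in substance. It places under the heading of events judged related those events for which the investigator chose a rating that points to another cause.

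Two reported results depend on the choice. One is the related-event line for a drug that, according to the protocol's risk assessment, has not yet been given to people infected with RSV. The other is the occurrence of AEs related to the viral challenge, a secondary endpoint in Protocol Section 3 and SAP Section 7.2.

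**Working it through.** The plan states no figure to reproduce. The check compares the sets of ratings counted as related, then works out what one participant contributes.

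**Sets of ratings counted as related** ('not given' in the text is read as 'Not assessed' in the shells)

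- A, Section 10.9.1: Unlikely, Possibly, Probably, Definitely, missing.
- B, overall TEAE summary footnote: Unlikely, Possibly, Probably, Definitely, missing.
- C, footnotes of Tables 14.3.1.4 and 14.3.1.5: Possibly, Probably, Definitely, missing.
- D, rows of the shared shell: Unlikely, Possibly, Probably, Definitely, missing.

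A, B and D are identical. A minus C = {Unlikely}. The conflict is therefore exactly one category, and the footnotes of Tables 14.3.1.4 and 14.3.1.5 are the outliers. Missing causality counts as related in every version, so it is not in dispute.

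**Against the protocol**

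- Section 10.3.2 calls an event an adverse drug reaction only when causality is at least a reasonable possibility.
- Section 10.3.6.5 says that a reasonable possibility needs supporting facts, evidence or arguments. It is not enough that a link cannot be excluded.
- Table 10-3 describes 'Unlikely' as pointing away from the IMP, and first mentions a plausible mechanism at 'Possibly'.

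Read together, these place 'Unlikely' below the reasonable-possibility standard. Set C fits that reading; sets A, B and D do not.

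**Size**

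Inputs: 40 participants planned per arm (SAP Section 6.1), all assumed to be in the safety population. Participants are counted once, at their strongest relationship (Section 10.9.1 and the shell footnotes).

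Let k be the number of participants in an arm whose strongest rating is 'Unlikely' and who have no event with a missing rating. Then

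related rate under A − related rate under C = k/40.

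For k = 1 this is 1/40 = 0.025, or 2.5 percentage points. The documents give no basis for k, so the total shift cannot be calculated. The same difference applies to each system organ class and preferred term count, with k taken within that class or term.

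**The case against.** The case for leaving the rule alone has some force. Three of the four SAP statements include 'Unlikely', which suggests a deliberately inclusive rule, in keeping with counting missing causality as related. On that view only one footnote and its challenge-agent copy need correcting. This stands as a legitimate second route, provided that the sponsor states the choice and its reason. It does not remove the need for a change.

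Four stronger readings are tempting, and the documents do not support them.

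- *The SAP breaks an explicit protocol rule.* It does not. The protocol gives a scale and no related/not-related cut, so the conflict is with the meaning of 'Unlikely' and the reasonable-possibility standard. Table 10-3 also covers only the IMP, so it cannot be turned against the challenge-agent table.
- *'Unlikely' ratings will be common in a challenge study, so the related rate will be greatly inflated.* No source supports this. Protocol Sections 10.3.1 and 10.3.6.2 keep many events with an obvious cause out of AE reporting: solicited viral symptoms, mild expected effects of nasal sampling, and expected pyrexia unless clinically significant. An event clearly due to something else may also be rated 'Not related', which every version excludes.
- *Inflation would hide a real difference between arms.* Equal additions to both arms leave the absolute difference unchanged; only the ratio shrinks. With assumed counts of 4/40 and 1/40 and 8 added to each arm, the result is 12/40 and 9/40. The difference is 3/40 = 7.5 points both times, while the ratio falls from 4 to 1.33. Safety analyses are descriptive (SAP Section 10.9), all TEAEs are tabulated regardless of causality, and the Table 14.3.1.4 shell shows each level separately.
- *Two tables will print contradictory overall totals.* The Table 14.3.1.4 shell has no row for participants with any related event. The mismatch would be in the class and term counts, and only if the footnote is followed.

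**Conclusion.** The point holds as an internal contradiction in the SAP, together with an undeclared grouping that fits poorly with the protocol's causality definitions. As written, the class and term counts in Tables 14.3.1.4 and 14.3.1.5 depend on which sentence is followed, and they may not agree with the overall summary. The supportable size is 2.5 percentage points per affected participant, assuming 40 treated per arm.

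It should be fixed but is not critical. It touches descriptive safety reporting only; the primary endpoint and every hypothesis test are unaffected.

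**What to change.** Before unblinding, use one definition of related (Possibly, Probably, Definitely or missing) in four places: Section 10.9.1, the overall TEAE summary footnote, the class and term header counts of Tables 14.3.1.4 and 14.3.1.5, and the footnotes of those two tables. The 'Unlikely' rows need not be deleted. They can stay as a separate row or table outside the related count, which keeps the by-arm information in view. Listing 16.2.7 already carries all five levels.

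If the sponsor deliberately keeps 'Unlikely' as related, state this with a reason in Section 11 and correct the footnotes of Tables 14.3.1.4 and 14.3.1.5 to match.

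Either route costs only edits to SAP text and shells. No data collection changes. Under the first route, the related counts fall by the number of participants whose strongest rating is 'Unlikely' and who have no event with a missing rating.

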10.9.2. Laboratory Variables

For all laboratory variables, baseline is defined as the assessment collected prior to the first administration of IMP.

The following parameters will be included within summary presentations (and presented in the units as shown):

- Haematology: platelet count ($10^9/L$), white blood cell (WBC) count (absolute) ($10^9/L$), neutrophils (% and absolute ($10^9/L$)), lymphocytes (% and absolute ($10^9/L$)), monocytes (% and absolute ($10^9/L$)), eosinophils (% and absolute ($10^9/L$)), basophils (% and absolute ($10^9/L$)), red blood cell (RBC) count ($10^{12}/L$), reticulocyte count (% and absolute ($10^9/L$)), haemoglobin (g/L), haematocrit (%), mean corpuscular volume (MCV) (fL), mean corpuscular haemoglobin (MCH) (PG), mean corpuscular haemoglobin concentration (MCHC) (g/L).
- Coagulation: prothrombin time (PT) (secs), activated partial thromboplastin time (APTT) (secs).
- Biochemistry: sodium (mmol/L), potassium (mmol/L), glucose (mmol/L), albumin (g/L), chloride (mmol/L), bicarbonate (mmol/L), calcium (mmol/L), uric acid (umol/L), total protein (g/L), creatinine (umol/L), total bilirubin (umol/L), indirect bilirubin (umol/L), direct bilirubin (umol/L), inorganic phosphate (mmol/L), blood urea nitrogen (mg/dL), C-reactive protein (CRP) (mg/L), gamma glutamyl transferase (GGT) (IU/L), alkaline phosphatase (ALP) (IU/L), alanine transaminase (ALT) (IU/L), lactate dehydrogenase (LDH) (IU/L), aspartate transaminase (AST) (IU/L), urea (mmol/L).
- Thyroid Function Tests (screening only): Free thyroxine (pmol/L), Thyroid Stimulating Hormone (mIU/L).
- Cardiac Enzymes: creatine kinase (IU/L), troponin T (ng/L).
- Urinalysis: colour, specific gravity, appearance, pH, dipstick presence of: blood, glucose, leukocytes, ketones, nitrite, protein, urobilinogen, bilirubin.

- Human Immunodeficiency Virus and Hepatitis A, B and C: HIV-1 and HIV-2 antibodies, hepatitis A antibodies (HepA IgM), hepatitis B surface antigen (HBsAg), hepatitis C antibodies (HCAb).

Observed parameter values and changes from baseline will be summarised appropriately for the above haematology, chemistry, coagulation and cardiac enzyme parameters. Any other laboratory parameters collected as part of the study will only be included in participant listings. Laboratory data collected in different units to that shown will be converted to the above specified units (if possible) for presentation in tables and listings.

Laboratory values outside the reference range will be identified in the participant listings as above or below the reference range. Laboratory values that are below the limit of quantification (BLQ) will be set to zero in computations for summary presentations but will be noted as BLQ in participant listings. Laboratory values that are missing will remain missing and will be noted as such in listings.

